#### 5.3. Randomization, blinding and treatment allocation

To prevent that large centers, > 100 expected subjects per inclusion period, are overrepresented we will randomize eligible patients admitted to these centers for inclusion 1:1.

#### 5.4. Study procedures

A physician from each participating country will be appointed as national coordinator. The researcher will enroll patients in the study. The participating centers will be visited by researchers to collect data of included patients. Before the start of data collection, a pilot study at the Amsterdam University Medical Center and the University Medical Center Groningen will be performed to detect and solve potential problems of the protocol.

#### 5.5. Withdrawal of individual subjects

Subjects can leave the study at any time for any reason if they wish to do so without any consequences.

#### 5.6. Replacement of individual subjects after withdrawal

There will be no replacement of an individual subject after withdrawal.

### 5.7. Follow-up of subjects withdrawn from treatment

There will be no follow-up of a subject after withdrawal.

#### 5.8. Premature termination of the study

There will be no reason for premature termination as no research related interventions will take place.

#### 6. SAFETY REPORTING

6.1. Temporary halt for reasons of subject safety

N.A.

6.2. AEs, SAEs and SUSARs

N.A.

**6.3.** Data Safety Monitoring Board (DSMB) and Safety Committee N.A.

#### 7. STATISTICAL ANALYSIS

## 7.1. Descriptive statistics

Descriptive statistics will be used to describe baseline characteristics, ventilation settings and parameters. Categorical variables will be expressed as n (%). A p-value < 0.05 is considered statistically significant. Data will be analyzed with R (R Core Team (2022). R: A language and environment for statistical computing. R Foundation for Statistical Computing, Vienna, Austria. URL https://www.R-project.org). No or minimal losses to follow–up for the primary and secondary outcomes are anticipated. In case of missing data, we will adjust complete–case analysis.

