### 4.4. Sample size calculation

To investigate the association of a limited set of pre-specified confounders with mortality in critically ill pediatric patients receiving invasive ventilation using logistic regression we estimate to need 100 events using the 10 event per variable of thumb. We aim to add 10 covariates to the model. With a conservative estimate of overall PICU mortality of 3% (1, 23) 3300 patients are needed for this analysis. With a conservative estimate of 50 participating centers, including 30 patients per inclusion period, the first analyses can be performed after the first year of inclusions. To explore differences between age groups (< 1 month, 1-11 months, 1-2 years, 3-6 years, 7-12 years, 13-18 years) and to do the same analysis in these groups we need around 19.800 patients in total. Taking a dropout of participating centers of around 30% into account, we expect to reach this sample size after including patients for eight years. After the first year, we will also start to include patients receiving other types of ventilatory support (i.e., noninvasive ventilation (NIV), high-frequency oscillatory ventilation (HFOV), continuous positive airway pressure (CPAP), bi-level positive airway pressure (BiPAP), and high-flow nasal oxygen (HFNO)). As some of these types, for example HFOV, are less frequently used and to be able to do the same analysis, we expect to need to include patients for approximately 10 years.

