### 5.1.2. Secondary ventilation settings and parameters

Secondary parameters are type of ventilatory support; type of airway management; type of ventilation mode; saturation of peripheral oxygen (SpO2); end-tidal carbon dioxide (EtCO2) and only if available blood gas analysis.

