## 5.2.2. Medical status

- Comorbidities (pulmonary, cardiac, neuromuscular, syndrome/genetic abnormalities, oncologic, organ transplant, chronic ventilation, mental retardation);
- Reason of ventilatory support; and
- Pediatric Risk of Mortality (PRISM) or Pediatric Index of Mortality (PIM) score, depending on which scoring system is used in the Pediatric Intensive Care Unit (PICU).

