### 5.2.4. Daily data collection

(this is for the first three full calendar days in the pediatric ICU)

At start of ventilation or at arrival when the patient has been intubated in another hospital, ventilation data will be collected directly and after 1 hour (name 'day 0'). Thereafter, ventilation data will be collected daily at a time point in the morning representing a steady state overnight, e.g., before the first morning blood gas is drawn, up to day 3, or the day of extubation or death.

- Type of ventilatory support: invasive ventilation; noninvasive ventilation (NIV), high–frequency oscillatory ventilation (HFOV), continuous positive airway pressure (CPAP), bi-level positive airway pressure (BiPAP), and high–flow nasal oxygen (HFNO);
- Type of airway management: intubation or tracheostomy (invasive); nasal/facial mask (non-invasive);
- Ventilation mode: volume controlled ventilation (VCV), assist-control (AC) or synchronized intermittent mandatory ventilation (SIMV); pressure controlled ventilation (PCV), AC or SIMV; volume support ventilation (VSV); pressure support ventilation (PSV); synchronized intermittent mandatory ventilation (SIMV) ± pressure support (PS); pressure regulated volume control (PRVC); neurally adjusted ventilatory assist (NAVA); NIV; HFOV; (n)CPAP; BIPAP; and HFNO;
- Ventilator settings: including but not restricted to: expiratory tidal volume (VTe) (mL) or inspiratory tidal volume (VTi) (mL) (only in case VTe is not available); PEEP (cm H2O); PIP (cm H2O) or Pplat (cm H2O) (cm H2O); level of pressure support above PEEP (cm H2O); trigger (flow or pressure, if flow then rate set); FiO2 (%); set and measured RR; I:E ratio; or inspiration time; SpO2 (%); EtCO2 (kPa);
- Arterial blood gas (ABG) analysis results or capillary blood gas (CBG) analysis results, only if available: pH; partial pressure of oxygen (PaO2) (kPa or mmHg); partial pressure of carbon dioxide (PaCO2) (kPa or mmHg);

- Imaging: X-ray (y/n). If yes, the first available X-ray after start of mechanical ventilation, will be assessed by the researcher (to prevent inter-observer variability) whether new opacities (unilateral or bilateral) consistent with acute pulmonary parenchymal disease are seen which are not due primarily to atelectasis or pleural effusion (y/n);

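### Complete-case analysis is the only missing-data rule and rests on outcome completeness alone, although covariates will be incomplete by center and clinical decision and the mortality model has no deaths to spare

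*Protocol*

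**What the plan says.** Section 7.1 states "In case of missing data, we will adjust complete–case analysis". The verb is presumably a slip; the sentence can only mean that complete cases will be analyzed. No alternative and no sensitivity analysis is named. The sentence before it gives the grounds: "No or minimal losses to follow–up for the primary and secondary outcomes are anticipated". Covariates and exposures are not mentioned.

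Other sections determine which data will be incomplete:

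- Section 5.2.2 collects a PRISM or a PIM score, "depending on which scoring system is used in the Pediatric Intensive Care Unit (PICU"). The instrument is set by the unit, not by the patient. Neither the score version nor the predicted probability of death is listed.
- Section 5.2.4 collects arterial or "capillary blood gas (CBG) analysis results, only if available", and section 5.1.2 repeats the condition.
- Section 5.2.4 records PIP or Pplat as alternatives, although section 5.1.1 lists both among the main endpoints.

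Section 7.3 plans propensity score matching and multivariate models without naming the adjustment variables. Section 4.4 sizes the mortality model: "we estimate to need 100 events using the 10 event per variable of thumb", with 10 covariates, 3% mortality and 3300 patients. Its only allowance for loss is about 30% dropout of centers, applied to the age-group total.

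**The concern.** The reason given for complete-case analysis addresses the wrong variables. ICU death and discharge will be known for nearly everyone; severity scores in a common form, blood gases and a particular airway pressure may not be. Complete-case analysis deletes a patient for any one missing model variable, so outcome completeness offers no protection.

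The expected gaps are also not random. The score type follows the center. A blood gas exists where a clinician chose to draw one and the unit could process it, so its presence plausibly tracks severity and resources. Deletion on these items can therefore change which patients and centers the estimates describe. That matters for a study that seeks independent associations with ICU mortality and, in section 2.1, geo-economic differences.

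The deleted patients also take their deaths with them, and the mortality model is planned at exactly the minimum number of events that the protocol sets itself.

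**Working it through.** **Reproducing the plan's figure (section 4.4).** Events needed = 10 per variable × 10 covariates = 100. Patients needed = 100 / 0.03 = 3333, against 3300 stated, which agrees within rounding. Deaths at the stated size = 3300 × 0.03 = 99, or 9.9 per covariate. At the planned mortality there is no reserve.

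**Effect of complete-case deletion.** Let m be the share of patients with at least one missing model variable, and assume that deaths are lost in proportion. Then deaths = 99 × (1 − m), and patients needed = 3300 / (1 − m). The protocol gives no value for m, so the range is assumed.

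| Assumed m | Deaths kept | Per covariate | Patients needed |
|---|---|---|---|
| 0% | 99 | 9.9 | 3300 |
| 10% | 89 | 8.9 | 3667 |
| 20% | 79 | 7.9 | 4125 |
| 30% | 69 | 6.9 | 4715 |
| 50% | 50 | 5.0 | 6600 |

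**What the severity score alone would do.** This depends on how it enters the model:

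- Both raw scores as covariates: a patient with only one is never a complete case.
- One raw score as covariate: only centers using it remain. If 30%, 50% or 70% of the 50 centers use it (assumed, with equal center sizes), 15, 25 or 35 centers remain, with about 30, 50 or 69 deaths.
- Raw values of both pooled in one column: no patient is lost, but two different scales are treated as one.
- Both converted to a common scale: nobody is lost through score format, and all 99 deaths remain.

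**Whether the planned mortality rate hides a reserve.** Section 4.4 calls 3% conservative and takes it from PICU patients overall, whereas the model is for invasively ventilated patients. To keep 100 deaths among 3300 patients after a loss m, mortality would have to be 100 / (3300 × (1 − m)): 3.4% at m = 10%, 4.3% at 30% and 6.1% at 50%. The protocol does not say what margin it expects.

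**Starting point after one year.** 50 centers × 30 patients × 2 periods = 3000 patients, or 90 deaths at 3%. Unless a third period takes place, the first-year count is below 100 before any deletion.

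**The case against.** A reader might infer that the adjusted models will drop whole centers and about half of the planned deaths. The protocol does not support that. It does not name the 10 covariates, does not place PRISM, PIM or blood gases in any model, and gives no share of centers per score. Section 5.2.2 can be read as a single severity item, which is not missing when either score is present. The covariate list and the way the scores are combined may properly stand in an analysis plan that is not shown. All this is right, and it makes the loss conditional.

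Section 7.4 runs an analysis only once its sample size is adequate, and recruitment lasts 10 years. A shortage of complete cases could therefore delay the pooled mortality model rather than force it through with too few deaths. This stands too, provided that adequacy is judged on complete cases, which the protocol does not say. Waiting restores the number of deaths but does not undo selection.

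Missing data may also be few: all items come from routine care, researchers visit the centers (section 5.4) and standard procedures are meant to limit gaps (section 9.2). These measures cannot produce a blood gas that was never drawn or a score that the unit does not use.

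Finally, complete-case regression is not always biased. If missingness is unrelated to death given the model covariates, the coefficients remain valid for the centers that stay. Exclusion by score type might come close to this; exclusion by whether a blood gas was drawn is less likely to.

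What survives all of these is narrower: the rule is already fixed, its stated grounds do not cover the variables at risk, and the event target has no allowance for their loss.

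**Conclusion.** The point holds in conditional form. The protocol commits to complete-case analysis on the strength of outcome completeness, while its own data collection leaves covariates and exposures incomplete in ways tied to center and clinical decisions. If a raw score or an optional item enters the adjusted or propensity models, patients or whole centers can be excluded selectively. Any such loss takes the mortality model below the protocol's own 10 deaths per covariate: to about 8.9, 6.9 or 5.0 for an assumed loss of 10%, 30% or 50%.

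These sizes rest on assumed loss rates, on deaths being lost in proportion to patients, and on 3% mortality. If the scores are harmonized and no optional item is used, score format costs nothing. It would therefore be too strong to call the severity adjustment unusable as written, or the sample size already broken. The change is still worth making, because it is cheap and because score version and predicted mortality may not be recoverable if they are not recorded during collection.

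**What to change.** 1. Replace the complete-case rule in section 7.1 with multiple imputation of covariates as the primary approach, with outcome and center in the imputation model, and keep complete-case analysis as a sensitivity analysis. Apply the same handling to the propensity score in section 7.3.
2. Record score type, score version and predicted probability of death in the eCRF.
3. Enter one harmonized severity variable: the logit of predicted mortality, with an indicator for score type. Harmonization should carry this rather than imputation, because few or no patients will have both scores from which one could be imputed from the other. An interaction between the logit and score type is optional.
4. Extend the expectation in section 7.1 to covariates. If complete-case analysis stays primary, state an expected loss m, divide the 3300 by (1 − m), and judge adequacy under section 7.4 on complete cases.

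The cost is modest analysis work, one or two eCRF fields and one or two parameters. By the protocol's rule, if the indicator is added on top of the 10 covariates, it raises the need to 110 deaths, or 110 / 0.03 = 3667 patients; with the interaction, 120 deaths, or 120 / 0.03 = 4000. Counting these terms within the 10 avoids the increase at the price of another covariate, which is why the interaction should be a choice and not a default.

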#### 7.2. Visualization of endpoints

Data will be visualized using distribution graphs for ventilation settings, variables and parameters, and Kaplan–Meier curves for events like liberation from the ventilator, discharge and death.

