### 5.1.3. Clinical outcomes

The clinical outcomes involve the incidence of Pediatric Acute Respiratory Distress Syndrome (PARDS); number of ventilation-free days at day 28; duration of ICU stay; ICU mortality and cause of death.

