### 5.2.5. Follow-up

Outcome data will be collected at ICU discharge:

- PARDS (y/n), according to the 2023 Pediatric Acute Lung Injury Consensus Conference (PALICC) definition (24);
- Air leak during ICU stay;
- Intubated (y/n), and if not, extubation date;
- Successful extubation; defined as no reintubation within 48 hours after extubation (y/n), if not: reason of reintubation;
- Alive (y/n), and if not, date of death in ICU; cause of death;
- Number of ventilation-free days at day 28 (zero in case of death or start ECMO);
- Date of discharge from ICU; and
- Destination after ICU discharge (other ICU, ward or home).

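### Section 7.2 names Kaplan–Meier for competing ICU events; if live discharges are censored, the ICU death curve overstates ICU mortality

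*Protocol*

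**What the plan says.** Protocol section 7.2 commits to "Kaplan–Meier curves for events like liberation from the ventilator, discharge and death". It names no other time-to-event method and gives no censoring rule, time horizon or treatment of competing events. Nothing elsewhere in the protocol supplies these for the curves.

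Three other sections bear on how the curves would behave:

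- Section 5.2.5: "Outcome data will be collected at ICU discharge". The death item reads "Alive (y/n), and if not, date of death in ICU; cause of death". No outcome collection after discharge is described.
- Section 5.1.3 lists "ICU mortality and cause of death" among the clinical outcomes.
- Section 7.1: "No or minimal losses to follow–up for the primary and secondary outcomes are anticipated".

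Section 5.2.5 does allow for death in one place: the ventilation-free-day count is set to zero for a child who dies or goes on ECMO. That rule belongs to that endpoint and does not carry over to the curves in 7.2.

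**The concern.** Under these definitions the events compete. A child who leaves the ICU alive can no longer have the recorded event of death in the ICU. A child who dies can no longer be liberated or discharged.

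Kaplan–Meier turns into an event probability only if censored patients keep the same future risk as those still observed. Children leave the ICU because they have recovered, so discharge is not censoring of that kind. Since almost no loss to follow-up is expected, nearly all censoring on a default death curve would be live discharge. One minus Kaplan–Meier would then not be the probability of dying in the ICU, and the figure could contradict the mortality percentage reported beside it.

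The size of the distortion depends on length of stay. If the curves were drawn for groups whose stays differ, they could separate even where mortality is the same.

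**Working it through.** **The protocol's own figure.** The protocol gives no number for the curves. The one stated figure that uses the mortality input is in section 4.4: "With a conservative estimate of overall PICU mortality of 3% (1, 23) 3300 patients are needed for this analysis". With "We aim to add 10 covariates to the model" and "we estimate to need 100 events using the 10 event per variable of thumb", 10 × 10 = 100 events and 100 / 0.03 = 3,333, against 3,300 stated. The figure reproduces to within rounding, so 3% is used below.

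**Inputs.** From the protocol: mortality m = 0.03 (4.4) and follow-up ending at ICU discharge (5.2.5). Assumed, because the protocol is silent: mean ICU stay L, the timing of deaths relative to discharges, and day 28 as the horizon (borrowed from the ventilation-free-day endpoint).

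**ICU death, constant hazards.** The death hazard is m/L, the live-discharge hazard (1 − m)/L, and their sum 1/L.

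- Discharges censored: 1 − KM(28) = 1 − exp(−28m/L)
- Cumulative incidence: CIF(28) = m × (1 − exp(−28/L))

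For L = 5: 28 × 0.03 / 5 = 0.168, so 1 − exp(−0.168) = 15.5%; and 0.03 × (1 − exp(−5.6)) = 3.0%.

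| Assumed mean stay (days) | 1 − KM at day 28 | CIF at day 28 | Ratio (unrounded inputs) |
|---|---|---|---|
| 3 | 24.4% | 3.0% | 8.14 |
| 5 | 15.5% | 3.0% | 5.17 |
| 7 | 11.3% | 2.9% | 3.84 |
| 10 | 8.1% | 2.8% | 2.86 |
| 14 | 5.8% | 2.6% | 2.25 |
| 21 | 3.9% | 2.2% | 1.77 |

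**Timing of death.** Constant hazards give deaths and discharges the same timing. A simulation relaxed this: 400,000 patients, log-normal stay with log-scale SD 0.9, 3% deaths. Ratios of 1 − KM to CIF at day 28:

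| Deaths occur at | Median stay 4 d | 6 d | 8 d |
|---|---|---|---|
| a quarter of survivors' stay | 1.31 | 1.28 | 1.27 |
| half | 2.03 | 1.87 | 1.79 |
| the same time | 3.92 | 3.13 | 2.59 |
| double | 7.24 | 4.78 | 3.65 |

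**If survivors stay in the risk set.** When the simulated survivors were kept event-free to day 28, Kaplan–Meier equalled the cumulative incidence (for example 2.9% against 2.9% at a median stay of 4 days with equal timing). The inflation disappears.

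**Discharge and liberation.** With deaths censored, the discharge curve gives 1 − exp(−28 × 0.97/L) against 0.97 × (1 − exp(−28/L)). At L = 7 that is 97.9% against 95.2%, a ratio of 1.028. The ratio is 1.030 at L = 5 and 1.021 at L = 14. A liberation curve with 3% deaths behaves the same way.

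**Higher mortality.** At 10%, the death-curve ratio runs from 4.30 (L = 5) to 2.10 (L = 14), and the discharge curve is 10.8% to 7.3% too high in relative terms.

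**The case against.** The strongest reply is that section 7.2 never says competing events will be censored. That is right: censoring at discharge is inferred from the named method and from where follow-up stops. An analyst who keeps discharged survivors at risk to day 28 gets the correct curve under the same name, and a SAP, which was not available for this check, might say so. What remains is that the protocol itself names the estimator, and the default use of that estimator on these data gives the wrong quantity for ICU death.

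A reader might go further and infer the following, none of which the protocol supports:

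- *The death curve will show several times the true mortality.* Neither length of stay nor timing of death is given. The calculated ratio runs from about 1.3 to about 8, and it is 1.0 if survivors remain at risk.
- *All three curves are equally wrong.* At 3% mortality only the death curve is materially affected.
- *The geo-economic and temporal comparisons rest on these curves.* Section 2.1 sets those aims, but no section stratifies or tests the curves. Section 7.2 concerns display only. Associations with outcome use regression and propensity matching (4.4, 7.3), and categorical outcomes are reported as counts and percentages (7.1).

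**Conclusion.** The point holds in conditional form. Kaplan–Meier is an unsuitable choice for ICU death when follow-up ends at ICU discharge. If live discharges are censored, the curve overstates ICU mortality at day 28 by about 2 to 5 times, assuming 3% mortality, constant hazards and mean stays of 14 to 5 days, and by about 1.3 times if deaths come very early. The liberation and discharge curves are about 2% to 3% too high in relative terms.

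The consequence is limited to a descriptive display. The mortality count and percentage, the logistic regression, the sample size and the main endpoint (ventilation settings and parameters) do not change. Should the curves be drawn by group, two groups with the same 3% mortality and mean stays of 5 and 14 days would read 15.5% and 5.8%, a gap produced almost wholly by length of stay (cumulative incidence 3.0% and 2.6%). That is a risk to guard against, not something the protocol plans. Severity is moderate; the evidence does not support treating this as an error that undermines the study's results.

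**What to change.** In section 7.2, replace Kaplan–Meier with Aalen–Johansen cumulative incidence curves and name the competing event for each: ICU death with live discharge competing; liberation with death competing; live discharge with death competing.

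An acceptable alternative for the death curve is to state that survivors discharged alive are kept event-free in the risk set to a fixed day, such as day 28, and to label the curve as ICU death so that it is not read as 28-day survival.

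Either way, state the horizon and say how transfers to another ICU, which section 5.2.5 records as a discharge destination, are counted.

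The cost is one or two sentences in the protocol or SAP. The data are those already planned, and standard R packages do the work.
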